1. PROJECT TITLE

Pulsed Electromagnetic Fields for Postoperative and Post-Amputation Analgesia: A Randomized, Participant- and Observer-Masked, Sham-Controlled Pilot Study

4. ESTIMATED DURATION OF THE STUDY

Three years (1 month preparation, 24 months enrollment, 11 months publication prior to closure)

5. LAY LANGUAGE SUMMARY OR SYNOPSIS (no more than one paragraph)

The moderate-to-severe pain many patients experience following surgery is often treated with opioids, which are associated with side effects such as nausea/vomiting, sedation, and respiratory depression (and a risk of abuse, dependence, and diversion). Potent site-specific analgesia with fewer side effects may be provided with peripheral nerve blocks. However, these too have limitations such as a duration of action measured in hours, while the pain from surgery is usually measured in days or weeks. Pulsed electromagnetic field therapy is an alternative method of pain control involving the application of electromagnetic energy. FDA-cleared devices have been in clinical use for over 70 years, demonstrating an extraordinary safety profile: these are noninvasive and nonpharmacologic devices, with no side effects, adverse events, or medication interactions; and the only contraindications are pregnancy and an implanted pulse generator such as a cardiac pacemaker. The device has no potential for dependence, abuse, or diversion. Until relatively recently, available devices consisted of a large signal generator and bulky coil applicator that were not portable and produced significant electromagnetic interference, making them impractical for common use. However, small, lightweight, relatively inexpensive, noninvasive, FDA-cleared devices that function for 30 days are now available to treat acute and chronic pain, decrease inflammation and edema, and hasten wound healing and bone regeneration. Therefore, it has the potential to concurrently improve analgesia and decrease or even negate opioid requirements following surgery, only without the limitations of opioids and peripheral nerve blocks. The purpose of this pilot study is to explore the possibility of treating acute postoperative and chronic post-amputation pain with pulsed electromagnetic field therapy, optimize the study protocol, and estimate the treatment effect in preparation for developing subsequent definitive clinical trials.

6. SPECIFIC AIMS

The proposed study will be a randomized, participant- and observer-masked, sham-controlled, parallel-arm, human participants pilot study with two primary aims:

Specific Aim 1: To determine the **feasibility** and **optimize** the protocol for subsequent clinical trials that will compare the addition of pulsed electromagnetic field therapy to usual and customary

analgesia following moderate-to-severely painful surgical procedures or post-amputation phantom and residual limb pain.

- Specific Aim 2: To estimate the treatment effect of adding pulsed electromagnetic field therapy to usual and customary analgesia on pain and opioid consumption following moderate-to-severely painful surgical procedures or post-amputation phantom and residual limb pain. This will provide an idea of the optimal surgical procedures and amputee characteristics amenable to this analgesic technique and allow determination of the required sample sizes of subsequent definitive clinical trials.
- Hypothesis 1: Pulsed electromagnetic field therapy decreases pain in the 7 days following moderate-to-severely painful surgical procedures or 28 days following application for postamputation pain.
- Hypothesis 2: Pulsed electromagnetic field therapy decreases opioid use in the 7 days following moderate-to-severely painful surgical procedures.

BACKGROUND AND SIGNIFICANCE 7.

The moderate-to-severe pain many patients experience following surgery is often treated with opioids, which are associated with side effects such as nausea/vomiting, sedation, and respiratory depression (and a risk of abuse, dependence, and diversion). Potent site-specific analgesia with fewer side effects may be provided with peripheral nerve blocks. However, these too have limitations such as requiring an anesthesiologist for administration, a duration of action measured in hours, and rendering the target area/limb insensate.

An analgesic alternative with few associated limitations is **pulsed electromagnetic field (PEMF)** therapy, also called pulsed short-wave therapy, pulsed radiofrequency energy therapy, and radiofrequency nonthermal diathermy.¹ Over the last 7 decades, PEMF has been used to treat acute and chronic pain, decrease inflammation and edema, and hasten wound healing and bone regeneration.¹ Possible mechanisms for the multiple clinical effects of PEMF are multifactorial, complex, and only partially understood.¹ The primary theory involves the promotion of calcium binding to calmodulin which activates endothelial and neuronal nitric oxide synthase isoforms, producing nitric oxide which has anti-inflammatory and analgesic effects, among other consequences

[figure not shown]
such as decreasing edema while increasing blood and lymph flow.¹

[figure not shown]
In 1947, the United States Federal Communications Commission assigned three frequencies for radiofrequency use in medical treatments: 40.68, 13.56 and 27.12 MHz.¹ Within just a few years, the first pulsed electromagnetic field generator was cleared by the United States Food and Drug Administration for use with patients using 27.12 MHz: the Diapulse.^{2,3}. Until relatively recently, available devices consisted of a large signal generator and bulky coil applicator that were not portable and produced significant electromagnetic interference, making them impractical for common use (Figure, right). However, over the past 70 years they have exhibited an extraordinary safety profile: these are noninvasive, nonpharmacologic devices, with no side effects, adverse events, or medication interactions; and the only

contraindications are pregnancy and an implanted pulse generator such as a cardiac pacemaker. Unlike opioids, there is no risk of abuse, dependence, and/or diversion.

More recently, small, simple, lightweight, battery-powered, noninvasive PEMF devices have received FDA clearance for use treating acute and chronic pain, including the ActiPatch and RecoveryRx for amputees and the initial 150 surgical subjects of Phase I (Model 088, BioElectronics, Frederick, Maryland; **Figure, below left**); as well as SofPulse for the subsequent 80 surgical subjects of Phase II (Endonovo Therapeutics, Woodland Hills, California; **Figure below right**). We will be using the devices for FDA-approved indications; in other words, on-label use.

First described as a therapy to treat postoperative pain in the 1960s,⁴ multiple investigations suggest analgesic benefits following various types of surgical procedures, including breast reduction,⁵ reconstruction,⁶ and augmentation;^{1,7} anterior cruciate ligament reconstruction;⁸ molar extraction;⁹ and cesarean section.¹⁰ Chronic pain conditions have also been treated with PEMF therapy, including knee osteoarthritis and failed back surgery syndrome.^{11,12} However, PEMF has not found widespread use, probably due to the cost and size of the initial large console devices; and later lacking credibility due to scant randomized data. What studies have been published generally involve small sample sizes,^{1,5,7} lack a control group,¹³ lack prospective registration,¹⁰ and/or authors with a significant conflict-of-interest.^{1,8,14-19}

Nevertheless, there appears to be extraordinary unrealized potential for PEMF to treat acute and chronic pain: it can be easily applied in less than one minute by a layperson using tape, induces no side effects (it induces no perceptible sensations at all), is completely noninvasive, is lighter and

thinner than many surgical bandages, may be applied to nearly any part of the body, functions through clothing or bandages, has only two contraindications (pregnancy and an implanted pulse generator), requires no intervention by patient or provider, has a duration of up to 30 days (unlimited duration using serial devices), has not resulted in any adverse events, has no abuse/dependence/diversion potential, and is relatively inexpensive compared to most other analgesics. *Due to its demonstrated benign profile and relatively low cost, PEMF could be applicable to nearly every painful surgical procedure and chronic pain condition, similar to acetaminophen and NSAIDs (only without every 6-hour patient/provider administration and the potential toxicity of acetaminophen and side effects/complications of NSAIDs).*

Consequently, we propose a randomized, participant- and observer-masked, sham-controlled, parallel-arm clinical pilot study to demonstrate feasibility and optimize the protocol as well as estimate the treatment effect to help design and power subsequent definitive, multicenter, randomized, controlled clinical trials. *The primary hypotheses are that PEMF decreases pain (and opioids for surgical patients) in the 7 days following moderate-to-severely painful surgical procedures or 28 days following application for post-amputation pain.*

8. PROGRESS REPORT

N/A

9. RESEARCH DESIGN AND METHODS

This will be a single-center (UCSD), randomized, participant- and observer-masked, sham-controlled, parallel-arm human subjects pilot study.

Enrollment. Participants will be consenting adults either (1) undergoing various surgical procedures usually resulting in moderate-to-severe postoperative pain, or (2) experience post-amputation phantom and/or residual limb pain. Study inclusion will be proposed (1) to eligible presurgical patients or (2) after an amputee contacts the investigators. If an individual desires study participation, written, informed consent will be obtained using a current UCSD IRB-approved ICF. The study population of interest includes adult women and men of all races, ethnicity, sexual identity, and socioeconomic status. Inclusion and exclusion criteria are listed in section #10 below.

Procedures. Following written, informed consent, we will record baseline anthropometric information (age, sex, height, weight, amputation details and current pain levels). Surgical participants will receive any standard peripheral nerve block(s) administered using bupivacaine or ropivacaine 0.5% with epinephrine (standard at UCSD) prior to undergoing their surgical procedure *per standard of care*.

Treatment Group Assignment. Each participant will be randomized to one of two treatment groups: *Active* or *Sham* treatment. For the initial 150 subjects of Phase I, there are sham RecoveryRx devices produced that are identical to active RecoveryRx devices, only they do not deliver PEMF. Randomization will be stratified by surgical procedure/amputation, in block sizes of 2. The computer-generated randomization lists will be created by the University of California San Diego Investigational Drug Service in a 1:1 treatment group ratio using opaque envelopes. For the initial 150 subjects of Phase I using RecoveryRx devices, the active and sham devices are indistinguishable in appearance, and therefore investigators, participants, and all clinical staff other than the individual who opens the randomization envelope and chooses a sham or active device will be masked to treatment group assignment for the duration of the data collection period. For the subsequent 80

subjects of Phase II, active SofPulse devices will be provided to patients randomized to the active treatment group; and sham RecoveryRx devices will be provided to the patients randomized to the sham treatment group.

Study intervention. For surgical patients of Phase I, the PEMF device (2 devices, if there are multiple incisions or the incision is larger than the device diameter; 3 devices for total knee and hip arthroplasty or spinal surgery) will be affixed over the primary wound area(s) using tape and activated prior to recovery room discharge (*Experimental*). For surgical patients of Phase II, a single PEMF device will be used for each participant due to their larger diameter and treatment area. For amputees, the device used is over-the-counter (ActiPatch, BioElectronics, Frederick, Maryland) and 2 devices (both the same treatment group) will be shipped to the patient either in or out of California who will then contact an investigator for assistance in self-placement of the device on the residual limb. The optimal location to treat phantom pain is currently unknown and will partially informed by the results of this pilot study, and patients will be encouraged to move the devices to a new anatomic location every two days until relief is experienced.

Supplemental analgesics. In addition to the PEMF device(s), participants will receive standard-ofcare supplemental analgesics which can include acetaminophen, ibuprofen, ketorolac, opioids, gabapentin (this is provider- and patient-dependent). *Therefore, all patients of this study—regardless* of the treatment arm they are randomized to—will continue to receive current usual and customary analgesia: all will receive the same combination of supplemental analgesics they would regardless of study participation (of note, amputees will be asked to continue their normal analgesic regimen, including any as-needed treatments). Participants (and their caretakers of surgical patients) will be provided with verbal and written instructions, and the telephone and pager numbers of an investigator available during business hours throughout the treatment period. Participants can shower with the device in place, but not submerge it during swimming or a bath, as advised by the manufacturer.

Surgical participants will be discharged with their PEMF device(s) *in situ* and a prescription for immediate-release oral opioid, preferably oxycodone 5 mg tablets, taken for breakthrough pain (surgeons occasionally prefer a different type of opioids such as hydrocodone, which is why we analyze the data using oral oxycodone equivalents). The PEMF devices will be removed by participants at home following Day 8 (SofPulse) or Day 30 (Actipatch/RecoveryRx) when the battery is exhausted (participants may remove them as early as Day 7, if they desire). Removing the devices encompasses tape removal and discarding in the trash (these are disposable, single-use devices).

Amputees will return their initial devices in pre-addressed and -stamped envelopes that we provide. They will be sent a second device which is the opposite treatment of the initial device: participants who initially received sham will subsequently receive active, and vice versa. These will be applied on Day 35 and the same protocol will be repeated as for the initial device, with additional data collected for 35 days after placement of the second device. The second device will be discarded in the trash.

Of note, if a device is reported lost or nonfunctional during the study, it will be replaced by the investigators by mail if more than 7 days of treatment remain.

Outcome measurements (end points). We have selected outcome measures that have established reliability and validity, with minimal inter-rater discordance, and are recommended for pain-related clinical trials by the Initiative on Methods, Measurement, and Pain Assessment in

Clinical Trials (IMMPACT) consensus statement. All data collection will be through standard UCSD EPIC notes and patient interviews in-person during hospitalization or *via* a telephone call for outpatients. Postoperatively, surgical endpoints will be recorded such as surgical duration. All pain scores will be measured using the Numeric Rating Scale (0: no pain, 10: worst imaginable pain). On Days 35 and 70, amputees will be asked if they would want to continue using the device; and on Day 28 surgical patients will be asked if they would want to use the device if they were to have the same surgery in the future? For Phase II surgical participants, Days 21 and 28 will be excluded due to the shorter treatment period (8 days) of this device relative to that used in Phase I. At all time points for amputees, phantom and residual limb pain will be distinguished and recorded separately.

	Surgical Patients Postoperative Days								Amputees Post-Application Days						
Time Point:															
	1	2	3	7	14	21	28	180	0	2	4	7	21	28	35
Opioid consumption	•	•	•	•	•	•	•	•	•	•	•	•	•	•	•
Average Pain [NRS]	•	•	•	•	•	•	•	•	•	•	•	•	•	•	•
Worst Pain [NRS]	•	•	•	•	•	•	•	•	•	•	•	•	•	•	•
Brief Pain Inventory,				_	_	-	•							•	
Short Form				•	•	•	•		•					•	•
Patient Global												_	•	•	
Impression Change										•	•	•	•	•	•
Sleep disturbances	•	•	•		•	•	•		•	•	•			•	
(#) previous night	•				-					-	-				-
Passive flexion					•										
(knees and hips)															

Summary of post-enrollment assessments (color added for clarity)

Primary end points: This is an exploratory pilot study to assist in planning subsequent definitive trials and we therefore have no data analysis plan. For surgical patients, the two outcomes of primary interest will be (1) the "average" and "worst" pain measured with the Numeric Rating Scale (included in the Brief Pain Inventory pain domain), and (2) opioid consumption within the first 7 postoperative days. For amputees, the outcome measures of primary interest will be (1) the change in "average" residual and phantom limb pain scores between baseline and Day 28 of the initial treatment, as well as (2) the Patient Global Impression of Change on Day 28 of the initial treatment.

For Phase II, there will be a total of 70 surgical participants, and these patients will be analyzed separately from Phase I surgical and amputation patients. Sample size calculations are based upon the hypothesis that pulsed electromagnetic field therapy decreases **pain** in the 7 days following moderate-to-severely painful surgical procedures. The primary outcome calculated as follows: for each participant all of the "average" and "worst" daily pain scores collected within the first 7 postoperative days will be summed. We will use these summed scores from participants having cholecystectomy (n=30), and hip and knee arthroplasty (n=40) to estimate a probable sample size.

We will consider a 33% reduction in pain scores to be the minimal clinically important difference [Farrar et al. J Pain Symptom Management 2003; 25: 406-11]. Based on values from patients receiving sham in Phase I, we anticipate the sham group to have an anticipated mean (SD) of 23.9 (12.3). Assuming a two-sided type I error protection of 0.05 and a power of 0.80, approximately 25 patients in each group are required (ClinCalc.com, accessed 2/23/23). To allow for a higher degree of variability than anticipated we will enroll a total of 70 participants in Phase II: cholecystectomy (n=30), and hip and knee arthroplasty (n=40).

Continuous, normally-distributed data will be reported as mean ± standard deviation. Nonparametric continuous or categorical data will be reported as median [10th-90th percentiles] or precents, as appropriate. Comparisons of independent samples will be performed using Student's t-test for parametric continuous variables or Mann-Whitney U test for nonparametric or categorical variables. The Chi Square test and Fisher's Exact test will be used for differences in proportions, as appropriate. P<0.05 will be considered statistically significant for the primary outcome. Results of comparisons in secondary outcomes will be interpreted as suggestive, requiring confirmation in a future trial before considering them as definitive.

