26. IMPACT ON STAFF

There will be no appreciable impact on nursing staff as the study intervention will take fewer than 5 minutes while the patient is in the recovery room and will not add to recovery room stay duration; and will not require any attention from the recovery room nursing staff.

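### In Phase II, fixed blocks of 2 with a different product in each arm make up to half of the assignments certain in advance to anyone who recognizes the preceding device

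*Combined protocol and SAP*

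**What the plan says.** Section 9 opens by describing the whole study as a "randomized, participant- and observer-masked, sham-controlled, parallel-arm human subjects pilot study". Under Treatment Group Assignment it gives one randomization rule: "Randomization will be stratified by surgical procedure/amputation, in block sizes of 2". Lists come from the Investigational Drug Service at 1:1, in opaque envelopes. No separate scheme is given for Phase II.

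The same paragraph supplies the masking mechanism for Phase I only: "For the initial 150 subjects of Phase I using RecoveryRx devices, the active and sham devices are indistinguishable in appearance". For Phase II, "active SofPulse devices will be provided to patients randomized to the active treatment group; and sham RecoveryRx devices will be provided" to the sham arm. Section 7 names a different manufacturer for each product, and Section 9 gives different removal days (Day 8 for SofPulse, Day 30 for RecoveryRx). Section 9 (Study intervention) cites the greater width of the Phase II device as the reason for using only one.

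On who does what:
- Section 11: investigators scan the surgery schedule, check eligibility, and call patients or pass names to a coordinator.
- Section 12: coordinators obtain consent on the day of surgery.
- Section 26: "the study intervention will take fewer than 5 minutes while the patient is in the recovery room".
- Section 9: for Phase I, one person opens the envelope and picks the device. The text does not say who does this in Phase II.

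**The concern.** A 1:1 block of 2 always holds one active and one sham assignment. Once the first is known, the second is fixed. Opaque envelopes do not protect against this, because the information comes from the device on the preceding patient. In Phase I, look-alike devices limit that knowledge to the envelope opener. In Phase II the products differ, and the block size is printed in the protocol.

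What is at stake is who enters each arm, which is a separate matter from whether outcomes are reported without knowledge of treatment. A recruiter who foresees the next arm can approach or defer a patient accordingly. Section 10 describes a convenience sample, so there is some discretion. Phase II is also the only part with a powered primary comparison, and Section 9 plans unadjusted two-group tests, so a selected difference between arms would pass straight into the result. No log of patients who were not approached is described.

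**Working it through.** **Inputs.** From Section 9: block size 2, ratio 1:1, and Phase II strata of 30 cholecystectomies and 40 hip or knee arthroplasties, total 70. Whether hip and knee form one stratum or two is not stated. The plan gives no predictability figure to reproduce.

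**Ceiling.** Suppose every preceding device is seen in time and the order within the stratum is known. A stratum of n then has floor(n/2) certain assignments.
- Strata 30/40: 15 + 20 = 35 of 70 = 50%.
- Strata 30/20/20: 15 + 10 + 10 = 35 of 70 = 50%.
- Strata 30/21/19: 15 + 10 + 9 = 34 of 70 = 48.6%. An incomplete pair only lowers the share.
- Best guess at 35 certain: (35 + 0.5 × 35)/70 = 75%.

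**Partial visibility.** Let s be the share of preceding devices seen in time. The certain share is 0.5s and the best guess is 0.5 + 0.25s. The documents do not give s; the values below are assumptions.

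**Comparison.** Fixed larger blocks help only partly. Full enumeration gives certain shares of 0.33 and 0.25, and best guesses of 0.71 and 0.68, for sizes 4 and 6. Randomly mixed blocks of 4 and 6 were simulated (2,000 list sets, equal chance of each size). The guesser was assumed to know the two possible sizes and to see each earlier assignment with probability s. The ranges cover strata 30/40 and 30/20/20.

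| s | Blocks of 2: certain of 70 | Best guess | Mixed 4/6: certain of 70 | Best guess |
|---|---|---|---|---|
| 1 | 35 (50%) | 75% | 4.0–4.1 (6%) | 68.6–68.9% |
| 0.5 | 17.5 (25%) | 62.5% | 0.20–0.27 | 58.5% |
| 0.25 | 8.75 (12.5%) | 56.25% | 0.01–0.03 | 54.8% |

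**Price in balance.** With mixed 4/6 blocks a stratum can end at most 2 apart at an even size, or 3 at an odd size.
- Two even strata: at most 4 apart, 37/33. The standard error ratio to 35/35 is √[(1/37 + 1/33)/(2/35)] = 1.0016.
- Three even strata: at most 6 apart, 38/32, ratio 1.0037.
- Strata 30/21/19: at most 2 + 3 + 3 = 8 apart, 39/31, ratio 1.0066.

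In 20,000 simulated list sets, the extreme splits occurred in 2% (37/33, strata 30/40) and 0.3% (38/32, strata 30/20/20).

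**The case against.** The strongest reply is that the path to harm is not documented. No section says that those who select, call or consent patients also see earlier devices, and silence about separate roles does not prove overlap. Section 11 describes contacting patients on the basis of eligibility, before the day of surgery. Devices go on in the recovery room, so some second patients will already have been contacted or consented. Outpatient follow-up is by "a telephone call for outpatients", which limits later sightings. All of this stands: it is why 50% is a ceiling and why no bias is quantified. It does not rule out deferral. The study has one center, no text separates the roles, and Section 26 keeps recovery room nurses out of device placement, which suggests that study staff do it.

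A second reply is that the root problem is the choice of two products, and that mixed blocks lower best guessing by only about 6, 4 and 1.5 percentage points at the three visibility levels. That is also correct. Mixed blocks remove near-certainty, not informed guessing.

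A third point is that Section 7 and another paragraph of Section 9 put Phase II at 80, not 70. The ceiling would then be 40 of 80, still 50%.

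Finally, this is a pilot and block size is a recognized trade-off. That argues for a modest rating, but not against a nearly free change.

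**Conclusion.** The concern holds. As written, up to 35 of 70 Phase II assignments are certain in advance to someone who knows the block size, the order within the stratum and the preceding device. The figure is slightly lower if a stratum ends mid-pair, and about 18 or 9 if half or a quarter of preceding devices are seen in time.

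Two links are inferred: that staff can tell the products apart by sight, which the stated width of the Phase II device supports, and that some recruiting staff see devices. The size of any resulting bias cannot be derived from the documents. This is an inexpensive improvement that should be made, not evidence that the trial is biased. Confidence is medium because of the second link.

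**What to change.** For Phase II, replace the block sentence with wording such as:

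> For Phase II, the Investigational Drug Service will generate 1:1 lists in randomly mixed block sizes within procedure; block sizes will not be disclosed to recruiting staff.

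Keep the sizes (for example 4 and 6) only in the Investigational Drug Service file. If Phase II has started, replace only the unused part of each list, after a completed pair.

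State who opens the envelope in Phase II. Where staffing allows, the person who opens it and applies the device should not select or consent later participants in that stratum. Otherwise, keep a dated log of eligible scheduled patients with the reason each was not approached.

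The cost is new computer-generated lists, one or two sentences, and some coordinator time if the log is used. The loss of precision from imbalance is at most 0.2% of the standard error with two even strata, 0.4% with three, and 0.7% in the odd-sized example above. The change does not restore masking in Phase II, which needs its own answer.

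### The participant- and observer-masked label has no stated basis in Phase II, where the device model identifies the arm and identical devices are claimed only for Phase I

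*Combined protocol and SAP*

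**What the plan says.** The masking label appears four times in the combined protocol and SAP, never limited to a phase:

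- Section 1 (title): "Participant- and Observer-Masked, Sham-Controlled Pilot Study".
- Section 6: "The proposed study will be a randomized, participant- and observer-masked, sham-controlled, parallel-arm, human participants pilot study".
- End of Section 7: "randomized, participant- and observer-masked, sham-controlled, parallel-arm clinical pilot study".
- Opening of Section 9: "randomized, participant- and observer-masked, sham-controlled, parallel-arm human subjects pilot study".

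The basis for the label is in Section 9, Treatment Group Assignment: "For the initial 150 subjects of Phase I using RecoveryRx devices, the active and sham devices are indistinguishable in appearance". From this the protocol concludes that investigators, participants and clinical staff are masked, except the person who opens the envelope and picks the device. The premise and the conclusion stand in one sentence, and that sentence covers Phase I only.

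The next sentence sets the Phase II rule: "active SofPulse devices will be provided to patients randomized to the active treatment group; and sham RecoveryRx devices will be provided to the patients" in the sham group. Section 7 names the manufacturer of the Phase II device: "SofPulse for the subsequent 80 surgical subjects of Phase II (Endonovo Therapeutics". The RecoveryRx device comes from a different company.

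Section 9, Outcome measurements, has data collected from clinical notes and by interview, in person for inpatients and by telephone for outpatients. The Phase II paragraphs of Section 9 define the primary outcome as the sum of the average and worst pain scores over the first 7 postoperative days, tested at P<0.05.

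**The concern.** In Phase I the argument for masking is complete: the devices look alike, so seeing one tells nobody the arm. In Phase II the protocol withdraws the premise, puts nothing in its place and leaves the label unchanged. Model and arm become the same thing. A staff member who has read Section 9 and sees the device during an in-person interview can infer the allocation.

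This matters because the Phase II primary outcome is a patient-reported score obtained by interview, and Phase II has its own sample size and significance test. If those who collect the scores know the arm, a difference between groups could include interviewer or reporting bias as well as any device effect. Nothing in the analysis could separate the two. If score collectors were unmasked, their masking could not be restored afterwards.

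**Working it through.** **Step 1. Compare the two phases in the text.**

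| Element | Phase I | Phase II |
|---|---|---|
| Active device | RecoveryRx | SofPulse |
| Sham device | RecoveryRx | RecoveryRx |
| Stated to look alike | Yes | No statement |
| Who is masked, by role | All but the envelope opener | No statement |
| Cover, separate assessor, script or masking check | None stated (identical devices serve) | None stated |

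**Step 2. Which differences between the products bear on the Day 1 to 7 scores?**

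- *Manufacturer (Section 7).* Relevant. The arms receive different companies' products.
- *Diameter (Section 9, Study intervention).* Weak evidence. A larger diameter is the reason given for using one device per Phase II participant, but the text does not compare the two arms' devices.
- *Working life (Section 9: Day 8 against Day 30).* Not relevant here. Both dates fall after the last score in the primary outcome.
- *Placement (Section 26).* Placement needs nothing from recovery-room nurses, which suggests that the study team does it. The documents do not say whether those who place devices also collect scores.

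**Step 3. How large could a bias be?** The plan gives no figure, so this step is an illustration.

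Inputs from Section 9: sham SD 12.3; sham mean 23.9; minimal important reduction 33%; two-sided alpha 0.05; 70 Phase II participants at 1:1, so 35 per arm. Within the first 7 days the assessment table has Days 1, 2, 3 and 7, with two scores each, so 4 × 2 = 8 scores.

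Assumption, not from the documents: knowledge of the arm shifts each affected score by 0.25 to 0.5 NRS points in favour of active.

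- Target difference: 0.33 × 23.9 = 7.89 points.
- Standard error: 12.3 × √(2/35) = 2.94 points.
- Shift in the sum = number of scores affected × shift per score. Noncentrality = shift ÷ 2.94. The rejection rate comes from the two-sided t-test with 68 degrees of freedom and no device effect.

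| Scores affected | Shift in sum | Share of 7.89 | Noncentrality | Rejection rate |
|---|---|---|---|---|
| 0 of 8 | 0 | 0% | 0 | 5.0% |
| 2 of 8, 0.25 each | 0.5 | 6.3% | 0.17 | 5.3% |
| 2 of 8, 0.5 each | 1.0 | 12.7% | 0.34 | 6.3% |
| 8 of 8, 0.25 each | 2.0 | 25.4% | 0.68 | 10.3% |
| 8 of 8, 0.5 each | 4.0 | 50.7% | 1.36 | 26.9% |

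The first row fits patients discharged before Day 1, if only in-person interviewers can be influenced: Section 9 follows outpatients by telephone, and Section 11 describes recruiting ambulatory patients. The 2-of-8 rows fit a single in-person interview on Day 1. The last two rows need bias in telephone scores as well.

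Sections 7 and 9 also give 80 as the Phase II number. With 40 per arm the standard error is 12.3 × √(2/40) = 2.75, and the four nonzero rows become 5.4%, 6.5%, 11.1% and 30.1%.

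**The case against.** The label claims masking of participants and observers only. It does not cover the person who places the device, so an unmasked placer is compatible with it if someone else collects the scores. Each participant sees one product, and Section 7 says of the therapy that "it induces no perceptible sensations at all". A telephone caller need not see the device, and because it works through clothing or bandages an in-person interviewer may not see it either. The protocol also names the two products openly. On this view the gap is one of reporting.

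Much of this stands. A reader might infer that Phase II is in fact unmasked, that every Phase II participant's scores are compromised, or that the label is false. The documents support none of these. They do not say who collects the scores. What participants are told about the two models cannot be judged, because the consent pages were removed before review. Nor can the products' appearance be compared, because the figures are not shown. The different battery lives might also seem to give the arm away, but they diverge only after the primary outcome is complete.

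The objection does not supply a mechanism. The circumstances that might preserve masking are incidental: the protocol does not invoke them as safeguards for Phase II, and nothing written prevents the person who placed the device from later asking for the pain scores. Lack of sensation also does nothing to mask an observer who can see the device.

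**Conclusion.** The point holds as a gap in the design as written. The only stated ground for masking applies to Phase I. In Phase II the model equals the arm, and no substitute safeguard appears anywhere in the documents supplied. The observer-masked claim for the Phase II primary test is therefore unsupported. It is not shown to be false, and unmasking is possible rather than demonstrated.

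The effect on the primary test is unknown. The range of 5.0% to 26.9% rests wholly on the assumed shift of 0.25 to 0.5 points per affected score and on how many scores are affected. The documents give neither a bias estimate nor a length of stay, so no row of the table is established. This should be fixed, and the case for doing so rests on the missing safeguard rather than on that range.

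**What to change.** In Section 9, Treatment Group Assignment, before Phase II scores are collected:

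1. State that existing team members who neither placed nor saw the device collect the Phase II Day 1 to 7 scores, by telephone where needed (including to inpatients), from a script that does not discuss the device.
2. State that participants are not told which model is active, as far as the approved consent form allows.
3. State by role who is and is not masked in Phase II. For example: *In Phase II the active and sham devices are not identical. Participants are not told which model is active. Staff who collect pain scores neither place nor see the device. The person who opens the envelope and staff who see the device may be unmasked.*
4. Report the non-identical devices as a limitation of the Phase II conclusion.

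If separate score collection is not adopted, limit the observer-masked label to Phase I in the title, Section 6, Section 7 and the opening of Section 9.

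The cost is some scheduling among existing staff, a short script and a weaker stated design claim for Phase II. The scheduling should be minor, but the documents give no staffing numbers, so that is an assumption. Devices, sample size and assessment days do not change.
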